9.0 SUBJECT REIMBURSEMENT

Subjects may be reimbursed for their time and travel and any expenses associated with each study visit, as allowed by study site policies. Subjects will not be reimbursed for those scheduled study visits that they do not attend.

10.0 STUDY WITHDRAWAL

Subjects may be terminated or withdrawn from the study for the following reasons:

- Voluntary withdrawal meaning that the subject voluntarily chooses not to further participate in the study
- *Lost to follow-up meaning that the subject is more than one month late (beyond the late visit window) to a study visit and 3 documented attempts to contact the subject are unsuccessful. A subject who misses a study visit but attends a subsequent visit will no longer be considered lost to follow-up.
- *In the physician's opinion, it is not in the best interest of the subject to continue study participation.
- Subject death.

*Where possible, subjects will be followed for safety to study completion. Safety follow-up will include a review of adverse events (AEs). A safety follow-up assessment may be performed either via a phone or email contact or a physician visit.

Any study subject who does not attend a scheduled follow-up visit should be contacted by site personnel to determine the reason for the missed appointment(s). The reason for the missed visit should be determined and documented in the subject's study records. All subjects enrolled (including those withdrawn or lost to follow-up) shall be accounted for with appropriate documentation.

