11.0 ADVERSE EVENTS

Adverse events (AEs) may occur during the treatment phase or during the follow-up phase. Adverse events occurring after the baseline assessment but before the treatment procedure will be documented in the subject's medical record but will not count as related to the study device or procedure.

Each adverse event will be recorded in the corresponding subject's CRF. Each adverse event will be judged by the Investigator as to its relationship and level of relatedness to the study device and/or study procedure. In addition, the Investigator will identify the date of onset, severity and duration of the AE. All adverse events will be monitored until they are adequately resolved or explained. If a subject reaches the 52-week follow-up visit and is experiencing a new or ongoing adverse event, the study sponsor should be contacted to discuss the need and/or methods for continued surveillance of the event.

The Investigator must submit to the Sponsor a report of any Serious Adverse Event (SAE), Serious Adverse Device Effect (SADE) or Unanticipated Adverse Device Effect (UADE) within 24 hours of knowledge of the event.

Sponsor Contact:	[name]
[contact]
[contact]
Email:	[contact]

In addition, the Investigator will report adverse events to the reviewing IRB / EC (as applicable) according to the local reporting requirements.

12.0 **RISK – BENEFIT ASSESSMENT**

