13.11 Primary Safety Endpoint Analysis

Safety will be assessed by characterizing the type and frequency of adverse events reported at or following the study procedure, and throughout the follow-up period. Event types include:

- Serious Adverse Events, including Deaths
- Serious Adverse Device Effects
- Unanticipated Adverse Device Effects
- Device Related Serious Adverse Events

The number of events as well as the percentage of subjects experiencing each event type will be calculated.

All adverse events will be analyzed for all enrolled subjects. Adverse events will be coded using a standardized dictionary, so that adverse events may be categorized for analysis at an appropriate level of detail. Listings will be provided to detail individual events. The number of subjects, number of adverse events, and the proportion of subjects reporting each adverse event will be summarized. Seriousness and severity of adverse events and their relationship to the device and/or procedure will be summarized. A time course of adverse events will be presented using the intervals:

- 0 days to 2 weeks
- 2 weeks to 4 weeks
- 4 weeks to 12 weeks
- 12 weeks to 26 weeks
- 26 weeks to 52 weeks

Narratives will be presented for all deaths, serious adverse events, serious adverse device effects, unanticipated adverse device effects, and subjects withdrawn due to an adverse event.

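### Section 10 leaves voluntary withdrawal out of its safety follow-up, so new adverse events after that exit are not actively sought and the crude proportions in 13.11 are likely to be biased downward

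*Combined protocol and SAP*

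**What the plan says.** Section 10.0 gives four reasons for leaving the study. Two carry an asterisk:

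- Loss to follow-up, which requires a visit overdue by over a month past its window and three recorded tries at contact that failed.
- Physician decision: "In the physician's opinion, it is not in the best interest of the subject to continue study participation".

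The matching note reads "Where possible, subjects will be followed for safety to study completion". It specifies an adverse event review, done by phone, email or a physician visit.

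Two reasons carry no asterisk: death, and "Voluntary withdrawal meaning that the subject voluntarily chooses not to further participate in the study".

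Section 11.0 adds a general duty: "All adverse events will be monitored until they are adequately resolved or explained". Section 13.11 sets the analysis: "All adverse events will be analyzed for all enrolled subjects". It summarises the number of events and the proportion of subjects reporting each, with a time course in five intervals up to 52 weeks.

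**The concern.** Adverse events are mainly found by asking at scheduled visits (Section 8.5 and Table 1). A subject who withdraws voluntarily has no further visits, and Section 10.0 puts no remote review in their place. The remote review goes instead to subjects whom the site has tried and failed to reach, and to those whom the physician removes. A voluntary withdrawer is often still in contact with the site when leaving, and might accept a short call while declining clinic visits. The plan does not have the site ask.

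This bears on the primary safety endpoint, which is the type and frequency of adverse events through the follow-up period. Treatment is one session and leaving the study does not reverse it. The possible effects listed in Section 12.1 include scarring that leads to obstruction, sensory change and dry eye. There is no control arm whose losses could serve as a comparison. If new events in withdrawers go unrecorded while the withdrawers stay in the denominator, the reported proportions are too low.

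**Working it through.** **Step 1. Does any other provision pick up a new event?** Take a subject who withdraws voluntarily after the 12-week visit and later develops a new event.

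- *Section 10.0 note:* does not apply, because this exit reason has no asterisk. The two asterisks and the single note match each other, so a text-extraction error is unlikely.
- *Section 10.0, missed visits:* the site contacts a subject who misses a visit, but to learn the reason, not to review adverse events.
- *Section 11.0, monitoring until resolved or explained:* applies to events already known. It does not create a search for new ones.
- *Section 11.0, 24-hour reporting of serious events:* runs from knowledge of the event, so it depends on someone telling the site.
- *Section 11.0, surveillance beyond the last visit:* only for a subject who reaches the 52-week visit.
- *Section 13.5:* handles missing data for the primary efficacy endpoint only.
- *Section 13.7:* counts withdrawals and actual visits, but is not tied to the adverse event percentages.
- *Section 13.11 narratives:* cover subjects withdrawn because of an adverse event, not events that start after exit.

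None of these has the site look for the new event.

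**Step 2. Effect on the reported proportion.** The documents give no figure for this point, so there is none to reproduce. Inputs:

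- *N = 50* (Section 13.3).
- *v*, the number of voluntary withdrawers: assumed 1 to 5. Five is 10% of 50, that is, the whole dropout and nonevaluable allowance of Section 13.3 taken as voluntary withdrawal. That allowance is not split by reason and belongs to the 12-week calculation, so it illustrates the scale and does not bound losses to 52 weeks.
- *p*, later-event risk in all other subjects: assumed 10%.
- *w*, later-event risk in withdrawers: assumed 40%, varied below.
- Capture is assumed complete in the others and nil in withdrawers after exit.

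Reported = (N − v)p / N. True = [(N − v)p + vw] / N. Shortfall = vw / N, which does not depend on p.

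- v = 1: reported 49 × 0.10 / 50 = 9.8%; true (4.9 + 0.4) / 50 = 10.6%; shortfall 0.8 points.
- v = 5: reported 45 × 0.10 / 50 = 9.0%; true (4.5 + 2.0) / 50 = 13.0%; shortfall 4.0 points.

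Shortfall in percentage points for other values of w:

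| v | w = 10% | w = 20% | w = 40% | w = 100% |
|---|---|---|---|---|
| 1 | 0.2 | 0.4 | 0.8 | 2.0 |
| 5 | 1.0 | 2.0 | 4.0 | 10.0 |

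The w = 10% column shows that the bias is downward even if withdrawers are at no higher risk than the rest. A treated withdrawer belongs to both the enrolled and the safety population (Section 13.4), so the choice between those denominators does not remove it.

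**The case against.** The strongest reply has four parts.

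1. *Events at exit are covered.* If a subject leaves because of a complaint that the site knows about, the event is recorded, monitored under 11.0, counted in the numerator and described in a narrative. **This stands.** A reader might infer that adverse events around voluntary withdrawal are never collected, or that Sections 10.0 and 11.0 contradict each other. The documents support neither reading: 10.0 does not forbid following an open event, and 11.0 requires it without exception for withdrawal. What remains is the new event after exit.

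2. *Counting withdrawers as event-free is not a rule of the plan.* **This stands as to wording.** It is the probable result of a crude proportion over enrolled subjects with no exposure or censoring rule, and should be described that way.

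3. *Voluntary withdrawal may be benign and rare.* It is tempting to call it the exit most likely to be driven by complaints, but the documents give no split of exit reasons, and physician decision, another exit that safety concerns may prompt, is covered. **This stands**, and it is why the size is unknown. The direction of the bias does not depend on it.

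4. *A plan may respect a subject's choice to stop taking part.* It may. The consent form is not among the documents reviewed and may already deal with later contact. But asking whether the subject is ending visits or all contact respects that choice too, and Section 10.0 does not provide for the question.

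It is also fair that 13.11 plans no safety test, confidence limit or acceptance threshold, so no planned decision turns on the shortfall. Nor is the note on lost subjects pointless: that status is reversible, and the note promises follow-up only where it is feasible.

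**Conclusion.** The point holds for new-onset adverse events after voluntary withdrawal. The plan as written does not have them sought, no other section closes the gap, and the crude proportions in 13.11 would probably be too low as a result. It does not hold for events known at exit.

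Under the assumed risks of 10% and 40%, the shortfall is 0.8 points with 1 withdrawer and 4.0 points with 5 of 50. Over the wider range shown it runs from 0.2 to 10.0 points, the top end requiring five withdrawers who all have a later event. These are illustrations: the number of withdrawers and both risks are assumptions. Sample size, significance level and power are unaffected. This is a gap in safety ascertainment that is cheap to close, not an error that invalidates the plan.

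**What to change.** In Section 10.0, extend the existing safety follow-up note to voluntary withdrawal for subjects who agree. At withdrawal, the site asks whether the subject is stopping visits only or all contact, and records the answer. Those who accept contact have the adverse event review already described there, by phone, email or visit, at the remaining scheduled time points through 52 weeks.

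In the same section, state that any event open at exit is followed as 11.0 requires, so that the two sections are read together.

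In Section 13.11, show the number of subjects with adverse event ascertainment in each interval beside the percentage, counting remote contacts as well as visits.

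The cost is a few sentences, a check that the consent form covers such contact, and a few extra contacts by existing site staff. Some withdrawers will decline, so some follow-up will stay missing, but the report will then show how much.

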11.0 ADVERSE EVENTS

Adverse events (AEs) may occur during the treatment phase or during the follow-up phase. Adverse events occurring after the baseline assessment but before the treatment procedure will be documented in the subject's medical record but will not count as related to the study device or procedure.

Each adverse event will be recorded in the corresponding subject's CRF. Each adverse event will be judged by the Investigator as to its relationship and level of relatedness to the study device and/or study procedure. In addition, the Investigator will identify the date of onset, severity and duration of the AE. All adverse events will be monitored until they are adequately resolved or explained. If a subject reaches the 52-week follow-up visit and is experiencing a new or ongoing adverse event, the study sponsor should be contacted to discuss the need and/or methods for continued surveillance of the event.

The Investigator must submit to the Sponsor a report of any Serious Adverse Event (SAE), Serious Adverse Device Effect (SADE) or Unanticipated Adverse Device Effect (UADE) within 24 hours of knowledge of the event.

Sponsor Contact:	[name]
[contact]
[contact]
Email:	[contact]

In addition, the Investigator will report adverse events to the reviewing IRB / EC (as applicable) according to the local reporting requirements.

12.0 **RISK – BENEFIT ASSESSMENT**

12.1 Potential Risks

Potential risks associated with the use of the InSeca ARC System do not differ from those of the commonly used devices and procedures to treat chronic rhinitis discussed previously, but due to the non-surgical nature of the therapy, small treatment area, low-power delivery and lack of need for general anesthesia, the overall risk to the patient may be less than from other procedures such as vidian neurectomy, septoplasty and/or functional rhinoplasty.

Potential risks associated with the use of the InSeca System and/or the associated local anesthetics are outlined below. Subjects will be monitored closely as part of this study to allow for detection of symptoms, should they be present. This, in turn, should allow for early treatment or intervention, if necessary.

The following are adverse events or side effects that may occur as a result of the treatment:

- Infection
- Bleeding (other than intra-treatment at treatment sites and greater than anticipated by the investigator)
- Mucosal changes
- Scar formation leading to nasal obstruction •
- Sensory changes at treatment site •
- Dry eye •
- External swelling of nose •
- Vasovagal response secondary to the procedure •
- Change in external shape or appearance of nose •

The following two tables list anticipated observations that are expected in and around the treatment Table 2 provides the incidence (reported as percentage of treated nostrils) observed in area. Clinical Study TP258, the nasal valve pivotal study. Table 3 provides the incidence observed in Clinical Study TP220, the rhinitis feasibility study. Anticipated observations will be assessed and recorded at study visits if they occur but, being anticipated as a result of the procedure, will not be considered adverse events unless they require mitigation by the treating physician or are greater in severity, duration or degree of incidence than anticipated. If one of these types of observations is deemed to be an adverse event, it should be recorded on the study Adverse Event CRF.

Observation	Post-Procee (% treated ne n = 99)	dure ostrils	4-Week Follow-Up (% treated nostrils n = 99)		12-Week Foll (% treated no n = 99)	ow-Up ostrils	26-Week Foll (% treated no n = 96)	ow-Up ostrils
Inflammation / redness	Not present Mild Moderate	53 42 5	Not present Mild Moderate	79 17 4	Not present Mild Moderate	89 9 2	Not present Mild Moderate	89 10 1
Swelling, edema	Not present Mild Moderate	45 52 3	Not present Mild Moderate	75 24 1	Not present Mild Moderate	89 9 2	Not present Mild Moderate	89 8 3
Nasal obstruction from tissue edema	Not present Mild Moderate	76 23 1	Not present Mild Moderate	82 13 5	Not present Mild	94 6	Not present Mild Moderate	90 9 1
Disruption of mucosal flow / crusting	Not present Mild Moderate	89 10 1	Not present Mild Moderate	62 34 4	Not present Mild Moderate	84 15 1	Not present Mild Moderate	91 8 1
Blanching	Not present Mild Moderate	29 58 13	Not present Mild	98 2	Not present Mild	98 2	Not present	100
Numbness	Not present Mild Moderate	56 30 14	Not present	100	Not present	100	Not present	100
Soreness, pain	Not present Mild Moderate	70 29 1	Not present Mild	94 6	Not present Mild	99 1	Not present	100
Bleeding at anesthetic injection site (no intervention)	Not present Mild Moderate	51 47 2	Not present	100	Not present	100	Not present	100
Bleeding at treatment site (no intervention)	Not present Mild	85 15	Not present	100	Not present	100	Not present	100
Saddle nose deformity	Not present	100	Not present	100	Not present	100	Not present	100
Bruising around orbital area	Not present	100	Not present	100	Not present	100	Not present	100

Table 2. Treatment Area Observations – TP258 Nasal Valve Pivotal Clinical Study

Table 3. Treatment Area Observations - TP220 Rhinitis Feasibility Clinical Study

Observation	Baseline (% treated nostrils n = 22)	Baseline2-Week Follow-Up $\%$ treated nostrils(% treated nostrils $n = 22$) $n = 20$)		1-Month Follo (% treated no n = 16)	ow-Up strils	3-Month Follow-Up (% treated nostrils n = 8)	
Swelling, edema	Not present9Mild91	Not present Mild	75 25	Not present Mild Not reported	75 12.5 12.5	Not present Mild	75 25
Blanching / color of mucosa	Pale pink 100	Pale pink Hyperemic	90 10	Pale pink	100	Pale pink Not reported	75 25
Obstruction	Not present91Present beyondmid-Meatus9	Not present Present in Ethmoid	90 10	Not present	100	Not present	100
Discharge	Not present45.4Thin36.4Thick18.2	Not present Thin Thick	60 35 5	Not present Thin	87.5 12.5	Not present Thin	87.5 12.5
Scarring / Crusting	Not present 91 Mild 9	Not present Mild Severe	35 50 15	Not present Mild	62.5 37.5	Not present	100

TP668 Ver. 27-NOV-2018

CONFIDENTIAL

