3.2.2 Surgical Treatment – Neurectomy

Vidian neurectomy is a surgical option to relieve nasal symptoms as the vidian nerve supplies autonomic input to nasal mucosa (as well as the palate and the lacrimal gland). While this surgery has been performed for over 50 years, it is known to be highly controversial since access to the nerve proves to be technically difficult and complications with numerous surrounding important structures can occur.^{9,10} Common procedural side effects include dry eyes, nasal dryness or crusting and mild pain, whereas more significant risks may include hemorrhage, vision loss and palate/lip/cheek numbness. In addition, improvement in symptoms is often unpredictable.⁹

An alternative neurectomy target is the posterior nasal nerve (PNN). The advantage of the PNN over the vidian nerve is its more limited innervation (it primarily stimulates the nasal mucosa) and its physical distance from other major nerve structures. As a result,

complications associated with PNN surgery are less significant and occur less frequently than those described for vidian nerve neurectomy,⁹ while still providing significant improvement in quality of life.¹¹

A recent publication describes the use of a cryosurgical probe to ablate posterior nasal nerve tissue.¹² This article details the long-term (1 year) results of treatment in a population of 27 chronic rhinitis patients, of which 48% had allergic rhinitis. Significant improvement in total nasal symptom score was seen between baseline score and each follow-up visit. Post-procedure adverse events resolved or improved by the 30-day follow-up visit. Overall, 74% of subjects had symptom improvement by 6 months post-procedure.

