7.4 Exclusion Criteria

A patient who meets any of the following criteria is not eligible to participate in the study:

- 1. Anatomic obstructions that in the investigator's opinion limit access to the posterior nose
- 2. Altered anatomy of the posterior nose as a result of prior sinus or nasal surgery or injury
- 3. Active nasal or sinus infection
- 4. Moderate to severe ocular allergic symptoms (such as eye tearing [epiphora], itching [pruritus], or redness [erythema])
- 5. History of significant dry eye
- 6. History of any of the following: nose bleeds in the past 3 months, rhinitis medicamentosa, head or neck irradiation
- 7. Known or suspected allergies or contraindications to the anesthetic agents and/or antibiotic medications to be used during the study procedure session
- 8. Known or suspected to be pregnant, or is lactating
- 9. Participating in another clinical research study
- 10. Other medical conditions which in the opinion of the investigator would predispose the subject to poor wound healing, increased surgical risk, or poor compliance with the requirements of the study

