8.2 Phase 2: Screening and Baseline Evaluation

During the screening/baseline visit in the study clinic, the Investigator or designated research staff will perform a formal evaluation of the study candidate for study eligibility, which will include a

history and physical examination of the nasal area, review of overall medical history, understanding of general health and discussion of any conservative measures used for rhinitis.

The following data will be collected:

- Patient demographics
- Medical history including prior tests and treatments for rhinitis
- Current medications and conditions for which they are prescribed
- Physical exam and vital signs
- Reflective TNSS questionnaire (symptom severity over the preceding 12 hours as reported by the subject)
- Investigator visual assessment (using an endoscope) of the target treatment area (posterior nasal nerve area) and any anatomy that might hamper necessary device access

Subjects who agree to participate and meet the enrollment criteria must be scheduled to undergo the study procedure **within 4 weeks** of the baseline visit.

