8.5 Types of Assessments

The following assessments will be obtained from the study subjects at the specified study follow-up visits:

Total Nasal Symptom Score (TNSS) – The TNSS is an instrument used to collect patient selfrated severity of four nasal symptoms: rhinorrhea, nasal congestion, nasal itching and sneezing. The FDA cites this as a preferred measure of efficacy in trials of drug treatments for allergic rhinitis¹⁷ and nonallergic rhinitis¹⁸. The TNSS requires the subject to rate four nasal symptoms (rhinorrhea, nasal congestion, nasal itching and sneezing) on the following 4-point scale:

- 0 = absent symptoms (no sign/symptom is evident)
- 1 = mild symptom (sign/symptom present, but minimal awareness; easily tolerated)
- 2 = moderate symptoms (definite awareness of sign/symptom that is bothersome but tolerable)
- 3 = severe symptoms (sign/symptoms that is hard to tolerate; causes interference with activities of daily living and/or sleeping)

For the purposes of this study, the subject will be asked to evaluate symptom severity over the preceding 12 hours.

Do not copy, distribute, or share with others without prior written authorization from Aerin Medical Inc.

Visual Assessment of Treatment Area – The target posterior nasal nerve area within each nostril will be visually assessed at baseline and following the treatment procedure at the time points described in Table 1. The use of an endoscope for visual assessment is required. For consistency in reporting across sites, a study CRF will outline specific observations to be assessed.

Video should be captured and archived during the endoscopic evaluation. These videos will allow for future evaluation or comparison, if necessary. If video capture is unavailable, representative still photographs may be collected instead.

Visual Analog Scale (VAS) for Pain Intensity¹⁹ – The Pain VAS will be used to rate pain associated with the treatment (i.e., in the treatment area) immediately following the procedure and at each follow-up visit through 12 weeks. Subjects will be asked to mark their pain level on a 10-cm line anchored by verbal descriptors: 0 = no pain and 10 = worst pain imaginable. The study staff will measure with a metric ruler from the 0, the beginning of the line, to the vertical mark made by the subject. The result, expressed in millimeters, will represent the subject's VAS Pain Score.

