Study-Specific Quality of Life (QOL) Questionnaire – The QOL questionnaire will be used to gain understanding of the impact of chronic rhinitis on the subject's daily activities, feelings, symptoms and medication use. The QOL will be completed by the subject both prior to the treatment procedure, and at the 12-week, 26-week and 52-week follow-up visits.

Subject Satisfaction Survey – The Satisfaction Survey will be used to assess patient acceptance of the treatment procedure and results. Subjects will be asked to complete the Satisfaction Survey at the 12-week and 52-week follow-up visits.

Adverse Event Evaluation – Subjects will be asked about possible side effects or adverse experiences related to the study procedure. All events will be documented on the Adverse Event Log and Adverse Event Case Report Form. Anticipated observations related to the study procedure will be tabulated but will not be categorized as adverse events unless they require mitigation by the treating physician or are greater in severity, duration or degree of incidence than anticipated. Refer to Table 2 for a listing of anticipated observations as well as anticipated frequency, severity and duration.

Medications – Updates to current medications and any new or changed medications will be requested at each follow-up visit. The medication log will be updated to reflect any changes. In addition, any medications required as a result of intervention related to the study procedure will be documented and correlated with the Adverse Event Case Report Form.

Table 1 outlines the assessments to be performed at each required visit and specifies the required visit windows.

TP668 Ver. 27-NOV-2018

Assessments	Screening / Baseline	Study Procedure (within 4 weeks of Baseline visit)	Immediately Post- Treatment	2-Week Follow-Up (+/- 3 days)	4-Week Follow-Up (+/- 1 week)	12-Week Follow-Up (+/- 2 weeks)	26-Week Follow-Up (+/- 3 weeks)	52-Week Follow-Up (+/- 4 weeks)
Demographics and Medical History	Х							
Physical Exam and Vital Signs	Х							
Medication Review	Х	Х		Х	Х	Х	Х	Х
Study Procedure		Х						
Endoscopic Assessment of treatment area (with video or photo capture)	Х	X*	X*	Х	Х	Х	Х	Х
rTNSS Score	Х			Х	Х	Х	Х	Х
Subjective Pain VAS			Х	Х	Х	Х		
QOL Questionnaire	Х					Х	Х	Х
Subject Satisfaction Survey						Х		Х
Adverse Event review			Х	Х	Х	Х	Х	Х
Pregnancy test (if female)		Х						

*Endoscopic assessment to be done both immediately prior to and after procedure

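### Dry eye is a named procedure risk, but no graded baseline or follow-up dry-eye item is specified, so mild new or worsened dry eye may be under-reported and hard to classify

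*Combined protocol and SAP*

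**What the plan says.** Section 12.1 names dry eye among nine adverse events or side effects that treatment may cause. Of the listed risks in general it says "Subjects will be monitored closely as part of this study to allow for detection of symptoms, should they be present". Section 3.2.2 says of vidian neurectomy: "Common procedural side effects include dry eyes, nasal dryness or crusting and mild pain". It notes that the vidian nerve also supplies the lacrimal gland, and gives the posterior nasal nerve's more limited innervation as its advantage.

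Section 7.4 excludes "History of significant dry eye", without defining the threshold. The other ocular exclusion also has a severity cut-off: "Moderate to severe ocular allergic symptoms (such as eye tearing [epiphora], itching [pruritus], or redness [erythema".

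At baseline, 8.2 provides for "history and physical examination of the nasal area, review of overall medical history", and the data collected include "Medical history including prior tests and treatments for rhinitis" and current medications with their indications. After treatment, 8.5 states: "Subjects will be asked about possible side effects or adverse experiences related to the study procedure". Table 1 schedules adverse event review immediately post-treatment and at 2, 4, 12, 26 and 52 weeks, and medication review at each follow-up visit. Section 11.0 has the investigator record onset, severity, duration and relatedness.

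**The concern.** Dry eye is the listed risk that bears most directly on the rationale in 3.2.2, because it would suggest an effect beyond the nasal mucosa. It also depends mainly on what the subject reports, whereas most of the other risks in 12.1 can be seen at endoscopy or by looking at the subject. The plan specifies structured measures for the nose and none for the eye.

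Two things are at stake.

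- **Sensitivity.** A general question restricted to experiences linked to the procedure asks the subject to make that link first. The adverse event definition in 31.0 requires no such link, and 11.0 leaves relatedness to the investigator.
- **Interpretation.** In a single-arm study where each subject is their own control (13.1), change in dry eye can only be read against the subject's own baseline. Subjects with milder dry eye or mild ocular allergic symptoms may enroll, and no baseline grade is specified. A broader adverse event question alone would not supply one.

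**Working it through.** The plan states no dry-eye rate or detection target, so there is no figure to reproduce. The check is mainly a comparison of the specified assessments.

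**Structured assessments**

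- rTNSS (8.5): four nasal symptoms, no eye item.
- Endoscopy (8.5): "The target posterior nasal nerve area within each nostril will be visually assessed at baseline and following the treatment procedure". It does not cover the eye.
- Pain VAS (8.5): pain in the treatment area.
- Tables 2 and 3: no dry-eye observation among those listed.
- Planned summaries (13.10 to 13.12): no ocular summary.
- Quality-of-life questionnaire (nine questions), nasal status assessment and case report forms: item wording is not in the documents, so an eye prompt can be neither confirmed nor ruled out.

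**General routes that can record dry eye**

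- Before treatment: medical history, current medications with indications, and the check of the two ocular exclusions. None is specified as a grade.
- After treatment: adverse event review at six time points, two of them (2 and 4 weeks) at or before the visit that completes phase 1, plus medication updates that could reveal a new eye treatment.
- Counting: dry eye is not in Tables 2 or 3, so the rule that keeps anticipated observations out of the adverse event counts does not remove it. A reported case would be recorded and summarized under 13.11.

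The gap is therefore the lack of a prompted, graded item with a baseline value.

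**Illustration of size**

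Inputs: n = 50 (13.3), taken as all treated and followed. The capture fraction s and the true rate p are assumptions, because the documents give neither.

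1. Upper limit when no case is recorded. Solve (1 − p × s)^50 = 0.05, so p = (1 − 0.05^(1/50)) / s.
   - s = 1: 1 − 0.05^(1/50) = 0.0582, or 5.8%.
   - s = 0.8: 0.0582 / 0.8 = 7.3%.
   - s = 0.5: 0.0582 / 0.5 = 11.6%.
2. Chance of at least one recorded case = 1 − (1 − p × s)^50.
   - p = 2%: 64% at s = 1; 40% at s = 0.5.
   - p = 5%: 92% at s = 1; 72% at s = 0.5.
   - p = 10%: 99.5% at s = 1; 92% at s = 0.5.

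Incomplete capture mainly weakens what a zero or low count can rule out. A common effect would probably still appear.

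**The case against.** The strongest case on the other side is that the protocol already has a working route. Overall medical history is reviewed, the exclusions oblige the investigator to consider dry eye and ocular allergy, subjects are asked about side effects at every post-treatment visit, and all events are logged with severity and relatedness. Consent under 8.1 covers the risks in detail, so subjects may know to mention an eye symptom. Section 3.2.2 attributes common dry eyes to vidian neurectomy and describes complications of posterior nasal nerve surgery as less frequent and less significant. The safety endpoint is descriptive, and at a true 10% rate with half of cases captured there is still a 92% chance of recording at least one.

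Most of this stands, and it rules out several stronger readings that a reader might infer:

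- *Nothing records dry eye at baseline or any visit.* Not supported: history, screening, adverse event review and medication updates all can.
- *It surfaces only if the subject volunteers it.* Not supported: a question is asked, though a general one.
- *The phase-1 review cannot see it.* Not supported: adverse event review takes place immediately post-treatment and at 2 and 4 weeks. It may miss milder cases.
- *The plan contradicts its monitoring statement in 12.1.* Not supported: that sentence is general, and scheduled review meets it in form.
- *Sensory change needs the same added item.* Not supported: numbness is already a graded observation in Table 2, and 12.1 says that anticipated observations are assessed and recorded at visits.

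The objection leaves the missing baseline grade unanswered. It also leaves the restriction of the question to procedure-linked experiences.

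**Conclusion.** The point holds as a limit on sensitivity and interpretation for one named risk. Mild new or worsened dry eye may be under-reported, and a report in a subject who entered with milder dry eye cannot be reliably classed as new, worse or unchanged. Zero cases in 50 would support an upper limit of 5.8% only with complete capture; at an assumed 80% or 50% capture the limit is 7.3% or 11.6%. Those fractions are illustrative and have no source in the documents. The conclusion also assumes that the case report forms and questionnaires, which are not in the documents, contain no dry-eye prompt; if they do, the point reduces to stating it in the protocol. The primary efficacy analysis is not affected. Priority: an optional, low-cost improvement.

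**What to change.** Add one subject-reported dry-eye item, graded none, mild, moderate or severe, at Screening/Baseline and at each follow-up visit in Table 1 (2, 4, 12, 26 and 52 weeks). In 13.12, tabulate shift from baseline by visit. Include the item in the phase-1 safety review after the 4-week visits, and state that worsening from baseline is recorded on the adverse event form.

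The cost is one question at existing visits and one shift table, with no new visit or procedure. The downside is that prompted questioning raises the number of mild reports, so prompted and unprompted reports should be distinguishable in the tables. The baseline grade is what makes the additional reports interpretable.
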